9.8.3 Records Retention and Requirements

The sponsor must archive all essential records and documents including but not limited to medical records, informed consent, and identification codes for subjects and other original records. These documents of the study will be retained in accordance with FDA record retention requirements, and will comply with CHOP policy A-3-9 for data retention.

9.8.4 Financial Disclosure

Financial disclosure information will be collected per Part 54 of Title 21 of the CFR and ICH E6. In addition, the site investigators must provide to the Study PI a commitment to promptly update this information if any relevant changes occur during the course of the investigation and for 1 year following completion of the study.

9.8.5 Regulatory Files

Prior to beginning the study, the principal investigator and site investigators will be asked to comply with ICH E6 8.2 and Title 21 of the CFR by providing the following essential documents, including but not limited to:

- An original investigator-signed Investigator Agreement page of the protocol
- An IRB-approved informed consent, samples of site advertisements for recruitment for this study, and any other written information regarding this study that is to be provided to the subject or legal guardians
- IRB approval of the protocol and amendments
- Form FDA 1572, fully executed, and all updates on a new fully executed form FDA 1572, Curriculum vitae (CV) for the principal investigator and each sub investigator listed on Form FDA 1572. Current licensure must be noted on the CV. They will be signed and dated by the principal investigators and sub investigators at study start up, indicating that they are accurate and current.
- Financial disclosure information to allow the sponsor to submit complete and accurate certification or disclosure statements required under Part 54 of Title 21 of the CFR and ICH E6. In addition, the Investigators must provide to the study PI a commitment to promptly update this information if any relevant changes occur during the course of the investigation and for 1 year following the completion of the study.
- Laboratory certifications and normal ranges for any test or assay being performed.

9.8.6 Monitoring

The study will be monitored by the sponsor and co-investigators. Prior to trial initiation, trial readiness will be confirmed by the Office of Research Compliance (ORC) of CHOP, as assessed by the Pre-Trial Monitoring Visit. Periodic institutional monitoring will also be conducted according to ORC guidelines.

The investigator will ensure that the study team monitors according to the relevant standard operating procedures (SOPs) and GCP guidelines on a periodic basis to verify that data entries into the CRF are correct and that the study is conducted in accordance with this protocol.

9.8.7 Modification of the Protocol

Protocol modifications that affect the safety of the subjects or that alter the scope of the investigation, the scientific quality of the study, the experimental design, dosages, assessment variable(s), the number of subjects treated, or the subject selection criteria may be proposed by the principal investigator and the Medical Monitor. Any change to the protocol can be made only in the form of a written amendment to this study protocol. Such amendments must be approved by the CHOP IRB, and the FDA notified.

9.8.8 Protocol Violations

Protocol violations or deviations are any non-adherences to the procedures outlined in this document and include, but are not limited to, late evidence of exclusion criteria,

missed evaluations, incorrect timing of evaluations or dosing, and intake of inadmissible medication. After a subject has been enrolled, it is the investigator's responsibility to make any reasonable effort to avoid and, if necessary, correct protocol deviations. Major protocol violations will be reported to the DSMB at the time of a meeting, the IRB and the FDA. All protocol violations will be listed and the admissibility of the subjects' data will be discussed with the Medical Monitor prior to the statistical analysis. In case any emergency or AE occurs that requires a protocol deviation in the particular case, the investigator should contact the Medical Monitor and DSMB as soon as possible to enable a decision on whether the subject's participation in the study may be continued.

[figure not shown]
9.9 Payment to Subjects/Families

There will be no payment or re-imbursement to families or subjects.

10 PUBLICATION

Data sets will be made available to the scientific community after publication(s) of planned analyses (as set forth in the protocol) of the clinical trial results or no later than 3 years after the final visit of the last participant to a clinical trial site, whichever comes first. Data obtained in this trial will be presented in national and international meetings and will be published in the medical literature with no delays. The investigators are not under any agreement with the provider of the drug to limit or delay the publication of data from this trial.

APPENDIX

Appendix 2. Study Timeline*

Procedures performed solely for research purposes are indicated in bold text

		Screening		Treatment						Early Termination	Safety Closeout
Visit number	Required	1	2		4 ^p		201 ^p	210º	212 ^p , 213°, 214 ^p , 215°, 216 ^p , 217°, 218 ^p , 219°, 220 ^p , 221°, 222 ^p , 223°, 224 ^p , 225°, 226 ^p , 227°, 228 ^p , 229°, 230 ^p ,231°	ET ^{ap}	801 ^q
	Optional ^q			3		5		205, 206,	212A, 213A, 214A, 215A, 216A, 217A, 218A, 219A, 220A, 221A, 222A, 223A, 224A, 225A, 226A, 227A, 228A, 229A, 230A		
Weeks from enrollment		4 to .5	0	2	4	8	12	16 to 52⁵	60 to 288°		292
Number of days at visit		28 to 2	Variable ^d	1-5	1-5	1-5	1-5	1-5	1-5	1-5	1-5
Visit window (days) ^e		2	+ 2	+ 2	+ 2	+ 2	+ 2	+ 5	+ 5	+ 5	+ 5
Informed consent	_	х									
Demographic characteristics	_	х									
Height	_	х	х	х	Х	Х	х	x	×	x	х
Weight	_	х	х	x	х	Х	х	х	x	x	x
Confirm tuberculosis test	_	X ^f									
Chest x-ray		Xa									
Electrocardiogra m (ECG)	_	Xr									
Echo cardiogram	_	Xr									
Review inclusion/		х									

exclusion											
criteria											
Medical history	-	Х									
Physical examination	_	х	Х	Х	Х	x	х	х	x	x	x
Vital signs	_	х	x	х	x	х	x	х	x	x	Х
Diary Scores	-	Xi	Х	Х	x	х	х	х	x	×	
Concomitant medications	_	х	Х	х	Х	x	х	х	Х	x	X
Previous Therapy		x									
AGS scale, GMFM-88 and functional neurologic testing, CLASI	_	X						Xs	Xs		
Adverse events	 		x	х	x	x	х	х	X	х	х
Dispense baricitinib ^k	_		x					x	x		
Laboratory											
Hematology	-	Xh	Xi	х	х	х	х	х	x	Xw	Xw
Serum chemistry ^v	_	X ^h	X ^j	х	Х	x	х	x	Х	Xw	Xw
Lipid panel		X ^h				x	х	х	x	Xw	
Urinalysis	-	X ^h	Xj	х	Х	х	х	х	x	Xw	Xw
IGF-1 [×]	-		х					x	x		
Vitamin D							Xw	Xw	Xw	Xw	Xw
HBsAg, HBcAb, HBsAb	 	X									
Hepatitis C antibody		XI									

HIV		XI									
		~									
HSV, EBV, CMV	-	XI	Xw								
Lymphocyte testing (T cell subset)		X ^h					x	x	x		
lgG	_	X ^h					x	х	X		
Cystatin C							Xw	Xw	Xw	Xw	Xw
Thyroid stimulating hormone and T4		Xf					Xw	Xw	Xw	Xw	Xw
Serum pregnancy test ^m		X ^h									
Urine pregnancy test ^m			х	Х	х	Х	х	х	x		
BK virus serum ^u		X ^h	Х	Х		Х	Х	х	x	Xw	Xw
Serum baricitinib concentration ⁿ			X	X	x	х	X	x	X	Xw	
IFN signaling score	_	X ^t	Х	Х	х	Х	Х	Х	x	Xw	Xw
Hand/wrist/finger s X-rays ^x			х					х	x		

Abbreviations: ET = early termination; HBsAg = hepatitis B surface antigen; HBcAb = hepatitis B core antibody; HBsAb = hepatitis B surface antibody; HIV = human immunodeficiency virus; SAVI = STING-associated vasculopathy with onset during infancy.

- a. Early termination visit is required if early termination occurs.
- b. Visits occur at approximately 4-week intervals during Weeks 16 through 52 (including both required and optional visits).
- c. Visits occur at approximately 12-week intervals during Weeks 60 through 288.
- d. Visit 2 encompasses the initial dosing period and can vary in time depending on whether the patient progresses through the first and second dose escalation during this period. Four days is the minimum time.
- e. Every effort should be made to schedule patient visits within the allowable visit window; however, if a patient visit is scheduled outside the visit window, it will not be considered a protocol violation.
- f. If results are available from testing within 1 month, then the patient will not have to be retested.
- g. Chest X ray will be performed on a clinical basis and results reviewed during screening. If chest x-ray was not performed clinically within 6 months prior to the study, it will be performed as part of the research study.
- h. If results are available from testing within 1 month or as part of the pre-screening period, then the patient will not have to be retested at Visit 1.
- i. At least 2 weeks of diary scores are required prior to beginning investigational product.

- j. Collect prior to each dose escalation. Investigator will review to ensure dose escalation is appropriate. Collect prior to the last dose given at Visit 2.
- k. Drug will be dispensed at visit 2, visit 204, and then every 6 months during onsite visits. However, when traveling to the investigative site is not considered safe for the patients due to unforeseeable events (see footnote o), such as public or personal health emergencies, the study drug may be dispensed for a longer time.
- I. If results are available from testing within the previous 3 months, then the patient will not have to be retested.
- m. For female patients of child-bearing potential: a serum pregnancy test will be performed at Visit 1 and a urine pregnancy test (local laboratory) will be performed at Visit 2 to determine study eligibility. At subsequent visits, a urine pregnancy test will be performed.
- n. Baricitinib concentration samples will be collected at on-site visits. Samples will be collected after beginning baricitinib therapy and at each dose escalation, and may be collected at each study visit for safety monitoring. However, when traveling to the investigative site is not considered safe for the patients due to unforeseeable events (see footnote o), such as public or personal health emergencies, baricitinib concentration samples will not be collected.
- o. These required visits should be performed at the investigative site. However, in some circumstances, unforeseeable events, such as public health emergencies, states of emergency related to civil unrest, or weather emergencies, or individual health emergencies (affecting the patient or a caregiver), may create situations where it is unsafe for patients and their families to travel to the study site for in person assessments. In that case, the visits will be conducted using video operations. The changes from an in person evaluation, including differences to the study outcome collection, will be reported as a minor protocol deviation to the IRB at the time of continuing review.
- p. These required visits may be performed at the investigative site or as a telephone visit. If a telephone visit is performed, lab samples should be obtained locally and the required labs to be reported are: total bilirubin, direct bilirubin, alanine aminotransferase (ALT), aspartate aminotransferase (AST), blood urea nitrogen (BUN), creatinine, and all hematology. In addition, physical examination is not needed if a telephone visit is performed.
- q. Optional visits may be performed at the investigative site or as a telephone visit but will not be considered a protocol violation if not performed. If a telephone visit is performed, lab samples should be obtained locally. Optional visits between weeks 60 to 288 would only be performed to allow patients to re-align with the initial in-person versus phone visit schedule, in cases where this schedule would be disrupted by an unforeseeable event (refer to footnote "o" for examples of such events) to enhance patients safety. For instance, if a patient were not able to come on-site for several months or years, an in-person visit may be necessary for the providers to assess the patient in-person.
- r. EKG and echocardiogram will be performed on a clinical basis and reviewed during screening.
- s. Functional outcome assessments will be conducted at baseline and every six months.
- t. Three baseline IFN scores will be collected, each at least 5 days apart and not more than 60 days before start of study medication.
- u. Patients will be monitored for BK viremia at baseline, and every six months until they reach two years of age. Over two years of age, complete follow-up BK testing will be performed if any of the following is observed: blood in urine (as defined by 5-10 RBCS in HPF), protein in urine (positive), decrease in eGFR (30 <60 mL/min/1.73 m²). Follow- BK testing includes urine and serum BK testing. Abnormal urine results with urinary tract infection, in the absence of change in eGFR, do not necessitate BK testing.
- v. The creatinine should be measured using the IDMS (Isotopic Dilution Mass Spectrometry) technique to monitor the eGFR if available. Other methods are allowed but are not preferred. Laboratory testing using other methods will not be used to monitor the eGFR.
- w. These labs may be drawn (optional).
- x. For bone growth monitoring, IGF-1 will be completed yearly, and hand/wrist/fingers X-rays will be completed at baseline, 6 months, 12 months and then every 12 months (not after a bone age demonstrating complete growth).

* Visit schedule will be extended beyond Week 288 to long term follow up if transition to commercial supply is not possible for a patient. Visit will then be extended until patient transitions to commercial supply. The same tests and procedures that were completed during the study will be continued. Visit numbers will continue per the same numbering logic (232, 233, 234...).

Appendix 3. Dose Escalation Schedule for Patients with eGFR ≥60 mL/min/1.73 m2 or Normal eGFR for Age <24 Months (see footnote below^c)

If a change in the patient's weight during the study would place the patient in a different weight range, changes over time are permitted.

		Morning Dose	Noon Dose	Afternoon Dose	Evening Dose	Total Daily Dose	Dosing Frequency
FR ≥ 60 mL/min/1.73	m ²						
5-< 10 kg	Initial	1 mg	1 mg	0 mg	1 mg	3 mg	TID
	Escalation 1	1 mg	1 mg	1 mg	1 mg	4 mg	QID
10-< 20 kg	Initial	2 mg	2 mg	0 mg	2 mg	6 mg	TID
	Escalation 1	2 mg	2 mg	2 mg	2 mg	8 mg	QID
20-< 40 kg	Initial	3 mg	-	0 mg	3 mg	6 mg	BID
	Escalation 1	3 mg	—	2 mg	3 mg	8 mg	TID
≥ 40 kg	Initial	4 mg	_	-	4 mg	8 mg	BID
	Escalation 1	5 mg	—	_	5 mg	10 mg	BID
	Escalation 2	6 mg	_	_	6 mg	12 mg	BID

BID = twice daily, eGFR = estimated glomerular filtration rate, QID = 4 times daily, TID = 3 times daily.

a If there was a change in the patient's weight during the study, this would place the patient in a different weight range.

b Based on adult patient data as there is little data available in pediatric patients.

c. For the purposes of this protocol, we will define age based parameters for eGFR as follows: Normal renal function not requiring dose adjustments if: >12 months: At least a GFR of >60 ml/min/1.73 m2. <12 months: A GFR of >40 ml/min/1.73 m2. Patients will be excluded from enrollment if baseline eGFR was <30 ml/min/1.73 m2

The creatinine should be measured using the IDMS (Isotopic Dilution Mass Spectrometry) technique to monitor the eGFR if available. Other methods are allowed but are not preferred. Laboratory testing using other methods will not be used to monitor the eGFR.

The population PK analysis was updated including data from 71 juvenile and adolescent patients with Chronic Atypical Neutrophilic Dermatosis with Lipodystrophy and Elevated Temperature (CANDLE), CANDLE related disorders, STING-associated vasculopathy with onset in infancy (SAVI), and Aicardi-Goutières syndrome (AGS). The analysis has shown that while kidney function, as expressed by estimated GFR, is a statistically significant patient cofactor of the PK characteristics of baricitinib in this multi-disease patient population, the effects of eGFR on the kinetics of this patient population were not clinically relevant as they relate to dosing and did not support dose adjustment for patients with eGFR less than 120 mL/min/1.73 m².

Appendix 4. Dose Escalation Schedule for Patients with eGFR 30- <60 mL/min/1.73 m2 or for Age <24 Months with abnormal eGFR (see footnote below^c)

If a change in the patient's weight during the study would place the patient in a different weight range changes over time are permitted.

		Morning Dose	Noon Dose	Afternoon Dose	Evening Dose	Total Daily Dose	Dosing Frequency
eGFR 30 - < 60 mL/min/ *	1.73 m ^{2b}						I
10-< 20 kg	Initial	1 mg	1 mg	0 mg	1 mg	3 mg	TID
	Escalation 1	1 mg	1 mg	1 mg	1 mg	4 mg	QID
20-< 40 kg	Initial	2 mg	-	_	1 mg	3 mg	BID
	Escalation 1	2 mg	_	_	2 mg	4 mg	BID
≥ 40 kg	Initial	2 mg	_	_	2 mg	4 mg	BID
	Escalation 1	3 mg	-	_	3 mg	6 mg	BID

BID = twice daily, eGFR = estimated glomerular filtration rate, QID = 4 times daily, TID = 3 times daily.

a If there was a change in the patient's weight during the study, this would place the patient in a different weight range.

[figure not shown]
b Based on adult patient data as there is little data available in pediatric patients.

c. For the purposes of this protocol, we will define age based parameters for eGFR as follows: Normal renal function not requiring dose adjustments if: >12 months: At least a GFR of >60 ml/min/1.73 m2. <12 months: A GFR of >40 ml/min/1.73 m2. Patients will be excluded from enrollment if baseline eGFR was <30 ml/min/1.73 m2

The creatinine should be measured using the IDMS (Isotopic Dilution Mass Spectrometry) technique to monitor the eGFR if available. Other methods are allowed but are not preferred. Laboratory testing using other methods will not be used to monitor the eGFR.

The population PK analysis was updated including data from 71 juvenile and adolescent patients with Chronic Atypical Neutrophilic Dermatosis with Lipodystrophy and Elevated Temperature (CANDLE), CANDLE related disorders, STING-associated vasculopathy with onset in infancy (SAVI), and Aicardi-Goutières syndrome (AGS). The analysis has shown that while kidney function, as expressed by estimated GFR, is a statistically significant patient cofactor of the PK characteristics of baricitinib in this multi-disease patient population, the effects of eGFR on the kinetics of this patient population were not clinically relevant as they relate to dosing and did not support dose adjustment for patients with eGFR less than 120 mL/min/1.73 m².

	r feeding and re	egurgitation score maximum				
lications:		Time medication was administered:				
	Lilly		Yes/No			
System	categories	Signs and Symptoms	103/100	Score		
	lity	Able to perform all activities of daily living or age appropriate milestones independently with no restriction		0		
	lide	Able to participate in the following with some level of disability: ambulation, communication or fine motor tasks at an age		_		
	Neurologic disability	appropriate level	choose one of	0		
		Requires functional or equipment support for any of the following: ambulation, communication or fine motor tasks at an age appropriate level				
	Irol	Dependent for all activities of daily living and unable to ambulate, communicate or perform fine motor tasks at an age		0		
Zei Z	appropriate level even with support		0			
		Cries but easily consolable		0		
	Crying	Excessive or high-pitched cry inconsolable for >2 minutes OR intermittently for <10 min	choose one of	0		
	CrV	Excessive or high-pitched cry inconsolable for >2 minutes AND intermittently for <10 min	these	0		
		Excessive or high-pitched not consolable (cries > 10 mins)		0		
S	ef pt	Sleeps >3 hours continuously during night		0		
anc	th c erru leep	Sleeps 2-3 hours continuously during night	choose one of	0		
urb	Length of uninterrupt ed sleep	Sleeps > or = 1 but <2 hours continuously during night	these	0		
dist		Sleeps <1 hours continuously during night		0		
em	ity it	no irritability		0		
syst	Excessive rritability	consoling calms individual in <6 minutes	choose one of	0		
Central nervous system disturbances Excessive Length of irritability uninterrup	consoling calms individual in 6-15 minutes	these	 			
	consoling calms individual in >15 minutes or not at all		0			
		No startle reflex Mild startle to noise		0		
	Strong startle reflex with noise	choose one of	 			
		Strong starter effex with noise including face grimacing, blinking and repeated jerks of arms	these	ŏ		
	Any startle without noise		0			
		No tremors (shaking, jittering, or shivering movements of the extremities that are not seizures)		0		
		Tremors when disturbed (awoken from sleep, moved, or stimulated)	choose one of these	0		
		Tremors when undisturbed	these	0		
		No tone issues	choose one of	0		
		Increased or decreased muscle tone (excessive stiffness or floppiness)	these	0		
	, eq	No convulsions or seizures				
	eneralize seizure		choose one of	0		
	Generalized seizure	Experienced convulsions or seizures	these			
	6			0		
	er	No fever (temperature less than 98.9 F)	choose one of	0		
	Fever	Low grade fever: 99 - 101 F (37.2-38.3 C)	these			
		Fever > 101.1 F (>38.4 C)	shaass and of	0		
		No feeding issues Poor feeding (infrequent/uncoordinated suck or dependent on g-tube feeding)	choose one of these	0		
		No regurgitation/vomiting	choose one of	0		
		Regurgitation/vomiting	these	 		
		Skin findings: no skin problem		0		
	Skin findings body	Skin findings: red patches which fade when pressed with fingers	choose one of	0		
5	sk bod	Skin findings: red patches not fading when pressed with fingers	these	0		
Other	+	Skin findings: chronic discoloration		0		
	lgs			~		
	Skin findings hands, face, ears	Skin findings: no skin problem	choose one of	0		
	n fir nds _. ea	Skin findings: red patches which fade when pressed with fingers Skin findings: red patches not fading when pressed with fingers	these	0		
	Ski ha	Skin findings: red patches not rading when pressed with fingers Skin findings: chronic discoloration	-	- 0		
		Skin findings: no skin problem in any location		0		
		Skin findings: red patches which fade when pressed with fingers in any location	choose one of	0		
		Skin findings: red patches not fading when pressed with fingers in any location	these	0		
		Skin findings: chronic discoloration in any location		0		

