 - An estimated glomerular filtration rate (eGFR) based on the most recent available serum creatinine of <40 mL/min/1.73 m² if greater than 2 year of age. eGFR will be calculated using the *Bedside Schwartz Equation:* eGFR (mL/min/1.73 m²) = (0.413 x height) / S_{Cr}, with height measured in cm, and serum creatinine (S_{Cr}) in units of mg/dL.
 - Children with an eGFR of <40 mL/min/1.73 m² will not be enrolled, unless <24 months of age in which case a cut off of <30 ml/min/1.73 m2 will be used due to age-based differences in normal eGFR. Normal eGFR of <60 ml/min/1.73 m² is common in children <12 months, and a normal eFGR <40 ml/min/1.73 m² is common in infants <3-6 months.
 - The creatinine should be measured using the IDMS (Isotopic Dilution Mass Spectrometry) technique to monitor the eGFR if available. Other methods are allowed but are not preferred. Laboratory testing using other methods will not be used to monitor the eGFR.
- Have any of the following specific Hematologic abnormalities on screening laboratory tests (Appendices 10, 11, 12):
 - Hemoglobin <7 mg/dL (70 g/L). In infants <2 mo of age, 8 mg/dL will be used as a threshold
 - Neutropenia (absolute neutrophil count [ANC] <500 cells/µL)
 - CD4 <250 cell/µl on lymphocyte subset testing (where Absolute CD4 count=Absolute CD3/CD4 count=CD3/CD4 count=CD4 count=Absolute CD3+CD4+ cells)
 - Thrombocytopenia (platelets <30,000/µL). Patients who are on

anticoagulation or having a history of life-threatening bleeding should be excluded if platelet count is <50,000/µL

- Have any of the following infectious risks:
 - Evidence of active infection, at the time of entry or during the screening period, that in the opinion of the investigator, would pose an unacceptable risk for participating in the study
 - Ongoing or incompletely treated severe or systemic infection, excluding cellulitis/osteomyelitis that is felt to be attributable to AGS
 - Have had symptomatic herpes zoster infection within 12 weeks prior to entry or during the screening period
 - Have a history of disseminated/complicated herpes zoster (for example, multidermatomal involvement, central nervous system involvement or systemic involvement including hepatitis or pneumonitis)
 - Have a history of active hepatitis B, hepatitis C, or human immunodeficiency virus (HIV)
 - Have had household contact with a person with active tuberculosis (TB) and did not receive appropriate and documented prophylaxis for TB

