4.2 Pre-screening period

The pre-screening period is applicable only to subjects not transferred from the JAGA Compassionate Use study (CHOP IRB Study #13205). The pre-screening period is a period from 2 weeks to 6 months during which the study will be discussed with the patient and caregivers. During this time, the study team may discuss the study with patients and families, and records of clinically indicated studies will be collected to help determine potential eligibility during the screening process. Individuals will undergo this pre-screening period if insufficient information about prior clinical care is available to the study team, for example, if their clinical care is received outside of the regional area. As part of the pre-screening period, patients or their guardians will undergo telephone consent, to explain the purpose and procedure of the study. Formal written consent will be obtained at Visit 1. During this period, blood and urine will be collected and daily diaries completed.

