4.4 Study Treatment Phase

4.4.1 Enrollment

Consent

Written informed consent from the patient/patient's parent or a legal guardian will be obtained in person by the study investigators prior to any study procedure, with the exception of blood and urine tests, and daily diaries, which may be completed from the pre-screening period, after verbal consent.

For the patients transferred from the JAGA Compassionate Use study (CHOP IRB Study #13205), written informed consent from the patient/patient's parent or a legal guardian will be obtained by the study investigators prior to any study procedure completed as part of this investigator-initiated study.

Additionally, all the JAGA subjects (including the patients who do not consent and transition to the investigator-initiated JAK inhibitor treatment in AGS study will be asked to sign a consent form to allow for their data collected as part of the compassionate use program to be used for data analysis as part of the investigator-initiated study. The JAGA subjects who do not transition to the investigator-initated study will sign a separate consent form while the subjects who transition will be re-consented with a revised informed consent form including mention of this data transfer. Statistical considerations of this data transfer are detailed in Section 6.

Inclusion criteria

Entered patients are eligible for enrollment into the study (that is, eligible to receive baricitinib) only if they meet inclusion criteria (Section 3.4.1) at the time of Visit 2 and don't meet the exclusion criteria listed in Section 3.4.2.

Exclusion from Study Enrollment

Entered patients are ineligible for enrollment (that is, ineligible to receive baricitinib) and should be discontinued from the study if they meet any of the exclusion criteria listed in Section 3.4.2.

Patients who are entered, but do not meet enrollment criteria, should be discontinued from the study. These patients can be re-entered into the trial (that is, be reconsented) if the investigator believes that the patient might meet enrollment criteria at a future date, taking into consideration the volume of blood required for rescreening. Patients will receive treatment as clinically indicated for infections regardless of treatment decisions for baricitinib.

Rationale for Exclusion of Certain Study Candidates

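### Appendix 2 footnote h lets results from a pre-screening period of up to 6 months replace Visit 1 testing, so a CD4 result that decides exclusion can be about 211 days old at first dose

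*Combined protocol and SAP*

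**What the plan says.** Section 4.2 sets the length of pre-screening: "The pre-screening period is a period from 2 weeks to 6 months". It provides for sampling in that time: "During this period, blood and urine will be collected and daily diaries completed". It gives no rule on when in the period the blood is drawn. Section 4.3 then adds a screening period of 2 to 28 days starting at Visit 1.

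In Appendix 2, footnote h is attached to the Visit 1 entries for hematology, serum chemistry and lymphocyte subsets, among others. It lifts the Visit 1 test "If results are available from testing within 1 month or as part of the pre-screening period".

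The exclusion criteria (Section 3.3.3) use these tests. Patients are excluded if they "Have any of the following specific Hematologic abnormalities on screening laboratory tests", and the list covers hemoglobin, neutrophils, CD4 and platelets. The renal exclusion uses the most recent available creatinine. Neither criterion gives a maximum age for the result.

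Section 4.4.1 makes patients eligible for baricitinib "only if they meet inclusion criteria (Section 3.4.1) at the time of Visit 2" and not if they meet an exclusion criterion. Appendix 2 marks the review of inclusion and exclusion criteria at Visit 1 only. For the Visit 2 safety samples, footnote j says "Collect prior to each dose escalation", and also asks for collection before the last dose given at Visit 2.

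**The concern.** Footnote h states a 1-month limit and then offers an alternative without that limit. Any child who goes through pre-screening can be admitted on the alternative, so for those children the 1-month limit has no force.

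The tests concerned include those that decide the laboratory exclusions, and these values can move. Section 4.6 says that AGS patients are at risk of hematologic disturbances, including neutropenia, and that baricitinib is itself associated with neutropenia and leukopenia. Entry is allowed from 1 month of age. The hemoglobin criterion changes at 2 months and the eGFR criterion at 24 months, so for an infant a gap of several months can cross an age band that the criteria use. If a value has crossed an exclusion limit since the sample was taken, the criterion describes the child's earlier state, and an ineligible child can be enrolled and dosed. eGFR also selects the dosing table (Section 4.4.2).

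**Working it through.** The documents state no maximum age of an eligibility result at first dose, so there is no figure to reproduce. The maximum follows by addition, with 1 month = 365.25/12 = 30.44 days.

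**Inputs**
- Longest pre-screening: 6 months = 6 × 30.44 = 182.6 days (Section 4.2).
- Screening, Visit 1 to first dose: 2 to 28 days (Section 4.3, Appendix 2).
- Stated limit in footnote h: 1 month = 30.4 days, applied at Visit 1.
- Next CD4 sample after Visit 1: Visit 201, week 12 = 84 days (Appendix 2).

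**Age of the oldest permitted result at first dose**
- Current text, full screening: 182.6 + 28 = 210.6 days; 210.6/30.44 = 6.9 months.
- Current text, shortest screening: 182.6 + 2 = 184.6 days = 6.1 months.
- 1-month limit only, full screening: 30.4 + 28 = 58.4 days = 1.9 months.

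Like for like, the alternative allows 6 months against 1 month at Visit 1 (6 times), or 210.6/58.4 = 3.6 times at first dose.

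**Interval between two scheduled CD4 results**
- Current text: 210.6 + 84 = 294.6 days; 294.6/7 = 42 weeks.
- 1-month limit only: 58.4 + 84 = 142.4 days; 142.4/7 = 20 weeks.

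**Is there a newer result before the first dose?**

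| Test | Exclusion criterion | Visit 2 sample | Tied to first dose? |
|---|---|---|---|
| CD4 | Yes | None; next at week 12 | No |
| Hemoglobin, neutrophils, platelets | Yes | Yes (footnote j) | No |
| Creatinine (eGFR) | Yes | Yes (footnote j) | No |

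I read the Visit 2 hematology superscript as j, as for chemistry, because footnote i concerns diary scores. Visit 2 is not a single time point: footnote d says that it covers the initial dosing period and lasts at least four days. Section 4.4.2 requires at least 72 hours on a dose before escalation, and Appendix 3 lists the initial dose separately from the first escalation. A sample taken only as footnote j requires can therefore come after the first dose.

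**Comparison with the other limits in Appendix 2**
Tuberculosis and thyroid results have 1 month (footnote f). Hepatitis C and HIV results have 3 months (footnote l). Baseline interferon scores must be no more than 60 days old at the start of medication (footnote t), although Section 5.2.18 says that the score will not be used for enrollment decisions. 210.6/60 = 3.5, so a CD4 result that does decide enrollment may be 3.5 times as old as a research marker that does not.

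**The case against.** The strongest reply is that footnote h waives testing at Visit 1 only. Hematology and chemistry are scheduled again at week 0, nothing stops a site from drawing them before the first dose, and any newer creatinine displaces the older one because the renal criterion takes the most recent. This stands. For these tests the fault is an unspecified order, not a missing sample. It does not help CD4, which has no Visit 2 sample.

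The 211 days is also a worst case. It needs blood drawn at the start of the longest pre-screening, no later test, and the full 28 days of screening. Pre-screening does not apply to patients transferred from the JAGA study and is used when the team lacks information on prior care. The waiver is permissive, and the investigator can exclude on health status, infection or laboratory values. All true, but these limit how often the gap arises and do not close it.

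Section 4.4.1 can be read as the real gate, with the missing Visit 2 mark a mere schedule omission. That is fair, but checking the criteria at Visit 2 does not help if the only CD4 value to check is months old. Sparing small children a draw is a visible reason for reuse, and it bears on the cost of the fix.

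A reader might infer more than the text supports:
- That first doses will rest on blood counts and creatinine 7 months old. The Visit 2 samples make this possible only.
- That IgG, BK virus and pregnancy testing are affected in the same way. IgG and BK virus have no exclusion cut-off; BK virus is scheduled again at Visit 2, as is a urine pregnancy test that footnote m uses for eligibility.
- That the text allows 7 times the stated limit. That sets age at first dose against a limit that applies at Visit 1.
- That an old value becomes the baseline for the hemoglobin work-up in Appendix 11. No section says so, and hematology is scheduled at week 0.

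**Conclusion.** The point holds in a limited form. The text permits a CD4 result of up to about 211 days at first dose, where the footnote's own 1-month limit would give about 58 days, and it schedules no replacement until week 12. For hematology and creatinine, the documents leave open whether a current result exists before the first dose. Separately, Section 4.4.1 and the Appendix 2 schedule disagree on the visit at which the criteria are reviewed.

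The figures assume that pre-screening ends at Visit 1 and screening follows it; if the 6 months included screening, the maximum would be about 183 days. They are upper bounds on what is allowed. The documents do not say how many children have a long pre-screening or how fast CD4 changes in them, so the number who could be wrongly enrolled cannot be estimated. The change is worth making because it is cheap and concerns who may be dosed. No efficacy or power figure depends on it.

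**What to change.** 1. In Appendix 2 footnote h, strike the pre-screening alternative so that the 1-month limit already stated applies at Visit 1, at least for lymphocyte subsets, hematology and serum chemistry. The maximum age at first dose falls from 210.6 to 58.4 days.
2. Reconcile footnote j with Section 4.4.1 by stating whether the Visit 2 hematology and chemistry sample is taken and reviewed before the first dose.
3. Mark the review of inclusion and exclusion criteria at Visit 2 in Appendix 2, so that the schedule agrees with Section 4.4.1.

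The cost is wording in one table row and two footnotes, plus one repeat of an already scheduled draw for non-JAGA patients with a long pre-screening. That draw should be checked against the research limits in Section 5.2.12 for the smallest infants. At the 4.5 kg entry weight these are 5 × 4.5 = 22.5 mL in a day and 9.5 × 4.5 = 42.75 mL over eight weeks. The documents give no draw volumes, so I cannot say how much room is left.
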